8.6.1. Analysis supporting primary objectives

Generalized mixed linear models will be used to compare the fat mass percentage change between the value measured at the end of the trial vs the baseline value. The analysis will include a fixed term modeling the change of fat mass between baseline and the second follow-up visit (after 1 year), as well as a random term accounting for repeated measurements on the

same participants. We hypothesize that the coefficient associated with the fixed term (fat mass) will be either equal to zero (no change) or negative (reduction of fat mass).

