1.2. Fasting Mimicking Diet

The fasting-mimicking diet (FMD) is a 5-day meal program to be consumed every 1 to 6 months based on an authorized healthcare professional's recommendation. It is designed to promote the body's natural ability to protect, regenerate and rejuvenate itself. In clinical studies, FMD has been shown to reduce abdominal fat and maintain healthy levels of blood glucose, C-reactive protein (CRP), and insulin-like growth factor 1 (IGF-1) (Wei et al., 2017). Well-designed clinical trials, such as the study conducted by Houston et al. utilizing an independent review board (IRB) approved protocol, have demonstrated the safety and short-term benefits of plant-based nutraceuticals and food restriction in individuals with chronic hypertension (Houston et al., 2014).

A large ongoing randomized, open-label trial aimed at evaluating the effects of two different dietary interventions, FMD and LD, on body composition and cardiovascular (CV) biomarkers in a real word population (NCT05698654) is actually ongoing. This trial started in January 2024 will enrol 501 adult subjects between the ages of 30 and 65: 167 subjects randomized to the FMD arm with a 5-day meal program once every three months for a 6-month period (arm 1); 167 subjects randomized to follow the FMD plus a Longevity Diet program (FMD+LD) for a 6-month period (arm 2); 167 randomized to the control group (arm 3) that will continue their usual diet. On 2024,410, participants were enrolled and randomly assigned to FMD, FMD + LD, or control arm. Although preliminary data demonstrated the beneficial effects of such nutritional plans on body weight, BMI, body composition, and cardiovascular (CV) biomarkers, limited data is available on the long-term effects of these powerful nutritional interventions.

2. Study Objectives/Endpoints

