2.2. Endpoints

- 2.2.1. *Primary endpoint*: maintenance of at least 50% of the fat mass lost during the previous trial and measured after one follow up year on FMD every 3 months
- 2.2.2. *Secondary endpoints*: maintenance of at least 50% of one or more risk factors improvements achieved during the previous clinical trial and measured after one year of follow up FMD cycles every 3 months including improvements in: body mass, body mass index, blood pressure, IGF-1, haemoglobin A1c, fasting glucose, LDL, total cholesterol, and C-Reactive Protein. Determine long-term trends in the reduction/stabilization in the use of antihypertensive and glucose-lowering drugs or other commonly used medications.

3. Study Design

Follow up clinical trial including participants of the approved studies “*Studio degli effetti della dieta mima-digiuno e della dieta della longevità sulla composizione corporea, fattori di rischio per malattie età-correlate e marcatori dell'invecchiamento in uno studio randomizzato*” and “*Studio degli effetti della dieta mima-digiuno e della dieta della longevità sulla composizione corporea, fattori di rischio per malattie età-correlate e marcatori dell'invecchiamento in uno studio randomizzato-2*” that will follow 5-day of the FMD meal program every three months, for one year.

Selection and withdrawal of subjects of the previous clinical study

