7.7. Study Discontinuation

The study will be discontinued for the following reasons:

- any clinical adverse event or serious adverse event, laboratory abnormality or inter-current illness which, in the opinion of the PI, indicates the continued treatment with study therapy is not in the best interest of the subjects.
- Termination of the study by the Sponsor.

8. Statistical Analysis plan

8.1.

All participants meeting the inclusion criteria will be considered. Based on the current drop-out rate of 21% and 18%, for FMD or FMD+LD, respectively, observed during the completed study “**Studio degli effetti della dieta mima-digiuno e della dieta longevità sulla composizione corporea, fattori di rischio per malattie età-correlate e marcatori dell'invecchiamento in uno studio randomizzato**” and assuming a similar drop out in the study: **Studio degli effetti della dieta mima-digiuno e della dieta longevità sulla composizione corporea, fattori di rischio per malattie età-correlate e marcatori dell'invecchiamento in uno studio randomizzato-2**” not yet completed, we can hypothetical foresee a maximum number of subjects of 267.

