8.6.4. Subgroup analyses

To explore the effect of treatment in subgroups, the estimated effect of the nutritional interventions will be estimated for each of the subgroups listed below will be derived. No adjustment for multiple comparisons will be made. Additionally, the frequency and percentage of subjects reaching the primary endpoint will be presented by treatment group for each of the subgroups based on the baseline measurements: baseline fat mass (\geq 20% and \geq 25% for men; \geq 30% and \geq 35% for women), age groups (30-50, 51-70 years), gender, baseline BMI (25-29.9; 30 and over);

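### Section 8.6.1 treats a zero fat-mass coefficient as a favourable result, which a test against zero cannot establish, and does not use the 50% retention limit of the primary endpoint

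*Protocol*

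**What the plan says.** Section 2.2.1 defines the primary endpoint as "maintenance of at least 50% of the fat mass lost during the previous trial", measured after one year of FMD cycles every three months.

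Section 8.6.1 describes the primary analysis. A mixed model compares fat mass (described in percentage terms) at the end of the trial with its value at this study's own baseline. It has a fixed term for the change to the one-year visit and a random term for repeated measurements. The hypothesis is: "We hypothesize that the coefficient associated with the fixed term (fat mass) will be either equal to zero (no change) or negative". The section names no margin, significance level or confidence-limit criterion, and does not mention the 50% limit.

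That limit comes back in section 8.6.4, where "the frequency and percentage of subjects reaching the primary endpoint will be presented by treatment group for each of the subgroups". This is descriptive, with no test and no target proportion.

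On size, section 8.1 says only that "we can hypothetical foresee a maximum number of subjects of 267". Section 8.7 applies the methods of 8.6.1 and 8.6.2 again, to participants who have completed six months.

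**The concern.** The favourable outcome in 8.6.1 has two parts. A negative coefficient can be demonstrated by a test. A zero coefficient cannot, because failing to reject zero fits no change, a modest regain, or a large regain measured imprecisely. If a non-significant coefficient is taken as the first part of the hypothesis, a positive estimate (fat regained) would count as support whenever its interval reaches zero.

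The hypothesis also differs from the endpoint. Section 2.2.1 tolerates regain of up to half the earlier loss, whereas 8.6.1 expects none. The two can therefore disagree in both directions: regain beyond half the loss can pass 8.6.1 through imprecision, and regain within the limit can fail it through precision.

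At stake is the trial's main claim, that fat loss is maintained. The protocol sets no minimum sample size that would limit the first error, and the six-month interim analysis, possibly on fewer people, uses the same hypothesis.

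**Working it through.** **1. The planned size.** Section 1.2 gives 167 participants per intervention arm in the parent trial. Section 8.1 gives the drop-out: "Based on the current drop-out rate of 21% and 18%, for FMD or FMD+LD, respectively".

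- FMD: 167 × (1 − 0.21) = 131.93
- FMD+LD: 167 × (1 − 0.18) = 136.94
- Sum: 268.87, or 131 + 136 = 267 when each arm is rounded down

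The plan's 267 is thus reproduced as a count of expected parent-trial completers. It is a ceiling, and no precision or power requirement stands behind it.

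**2. Chance of a non-significant coefficient when fat is regained.** The protocol gives no earlier fat loss, SD of change or significance level. The following are assumptions: two-sided 5%; a paired comparison of baseline and 12 months, standing in for the mixed model; changes in kg; and, for this illustration only, a new baseline equal to the value at the end of the parent trial.

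With true mean regain μ, SD of change s and n participants, T follows a non-central t distribution with n − 1 degrees of freedom and non-centrality δ = μ√n / s. Then

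P(non-significant) = P(|T| < t₀.₉₇₅,ₙ₋₁).

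For μ = 1.2 kg after a 2 kg loss (60% regained, so beyond the limit on average) and s = 4 kg:

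| n | δ = 0.3√n | P(non-significant) |
|---|---|---|
| 267 | 4.90 | 0.2% |
| 100 | 3.00 | 16% |
| 50 | 2.12 | 45% |

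Sensitivity to the SD: with s = 3 kg the figures are 2% (n=100) and 21% (n=50); with s = 5 kg they are 34% and 62%.

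Sensitivity to the loss: for μ = 0.6 kg after a 1 kg loss (again 60%) and s = 4 kg, δ = 0.15 × √267 = 2.45 and P = 31.5% at n=267; at n=100 it is 68%.

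**3. Where the sample-size effect stops.** If the true mean change is exactly zero, the chance that the coefficient is not significantly above zero is 97.5% at every n. If fat mass truly falls, it is near 100% at every n. The advantage of a small or noisy study exists only for positive true regain.

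**4. The opposite disagreement.** Take μ = 0.8 kg after a 2 kg loss (40% regained, within the limit on average), s = 4 kg and n = 267. Then δ = 0.2 × √267 = 3.27, and the regain is significant in 90% of studies. The hypothesis of 8.6.1 would be contradicted although the mean meets the 50% limit.

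**5. A margin criterion under the same assumptions.** Require the upper limit of the two-sided 95% CI for mean regain to lie below M = 1 kg (half of 2 kg), with s = 4 kg.

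| True mean regain | n=267 | n=100 | n=50 |
|---|---|---|---|
| 0 kg | 98% | 70% | 41% |
| 1.0 kg (at the margin) | 2.5% | 2.5% | 2.5% |
| 1.2 kg | 0.3% | 0.7% | 1.1% |

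For true regain below the margin, precision now helps a maintenance claim. At the margin the false-success rate is fixed at 2.5%, and beyond it the rate is lower still.

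**The case against.** The strongest objection is that 8.6.1 states an expectation and not a decision rule. A reader might infer that the protocol declares success on any non-significant coefficient. It does not say so, and an analyst who reported the estimate with its interval would also comply. A significance level or interval criterion may sit in an SAP that is not at hand. This stands, and the point is conditional for that reason. It does not rescue the sentence, because the hypothesis as fixed includes a value that the named method cannot confirm, and an SAP would have to replace it.

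A reader might also infer that the protocol sets no limit on tolerable regain. Section 2.2.1 sets one, and 8.6.4 would show the share of participants who meet it, by subgroup. The fault is narrower: 8.6.1 leaves the limit out.

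A third tempting reading is that a smaller study always succeeds more easily. Step 3 shows that this needs positive true regain.

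Finally, the larger percentages come from assumed kilograms and from sample sizes of 50 and 100 that the protocol never names. In the main scenario the risk at n=267 is 0.2%, and about 0.8% at n=214 (267 less roughly 20% drop-out). This also stands. However, 267 is a maximum: enrolment depends on willingness and on having achieved the parent study's objectives (section 3.2), and the second scenario gives about 31% even at 267.

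**Conclusion.** The concern holds in conditional form. Section 8.6.1 includes in its favourable outcome a value that a test against zero cannot establish, and it does not use the endpoint's own limit. These two statements rest on the text alone.

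That imprecision could pass for maintenance further requires that non-significance is read as no change and that true mean regain is positive. The size of that risk cannot be fixed from the protocol. Under the assumptions shown, it runs from 0.2% at full enrolment with 1.2 kg regain and SD 4 kg, to 45% at n=50, and it is about 31% at full enrolment if the regain is 0.6 kg. The direction does not depend on the assumed values; the percentages are illustrations. The reverse error, significant regain that is still within the 50% limit, becomes likelier as the study becomes more precise.

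**What to change.** Replace the hypothesis sentence in 8.6.1 with a criterion tied to 2.2.1. It should be computed from fat mass at parent-trial start, parent-trial end and 12 months, all in one unit:

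> Maintenance is concluded only if the upper limit of the two-sided 95% CI for mean fat-mass regain from the end of the parent trial to 12 months is below half the mean fat mass lost in the parent trial. The proportion of participants retaining at least 50% is reported overall with its 95% CI. Further reduction is concluded only if the upper limit for change from the new baseline is below zero. A non-significant coefficient is not evidence of maintenance.

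The starting point matters. Sections 3.1.1 and 3.2 allow up to six months between the end of the parent trial and the new baseline, so a margin applied to change from the new baseline would miss regain in that gap. The unit matters too: 8.6.1 speaks of percentages, while the endpoint concerns fat mass lost. The overall proportion is needed because a mean can pass while many individuals do not retain half their loss.

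The cost is a wording change, linkage to each participant's parent-trial values, and a decision on the unit. The downside is that a small or imprecise sample can no longer support a maintenance claim: in step 5, with no true regain, success falls from 98% at n=267 to 41% at n=50.

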3.3. Scheduled clinical visits

The assessment schedule (Table 1) lists all the assessments and when they are to be performed. Subjects will meet with study staff. When the visit doesn't include blood collection or BIA the visit can be made remotely. During the clinical visits, staff will review calendars, assess for signs and symptoms of adverse events, review compliance to the study product and answer any questions from the subject. Eligible participants will receive 3 different visits (Baseline visit (t0), and two follow-up visits (after 6 and 12 months from the baseline). Eligible participants will be telephonically contacted at the end of each FMD cycle (day 6) in order to assess signs and symptoms of adverse events, compliance to the nutritional intervention (see Appendix A, B), to answer to the questionnaire for dietary recall (see Appendix C).

4. Table 1 reports the timeline of the clinical visits and the activities scheduled. All data obtained from these assessments must be supported in the participant's source documentation.

	Screening Visit	Baseline visit (T ₀)	Follow-up visit 1 (T ₁)	Follow-up visit 2(T ₂)
Informed Consent	✓			
Review Eligibility Criteria	✓			
Start of intervention				
Physical examination ¹		✓	✓	✓
Vital Signs ²	✓	✓	✓	✓
BIA		✓	✓	✓
Peripheral Blood for genetic analysis		✓		✓
Hematological analyses ³		✓		✓
Pregnancy test	✓	✓		✓
AE and SAE collection		✓	✓	✓
Primary and secondary endpoints assessment		✓	✓	✓
Medications	✓	✓		✓

¹ height, weight (dress weight), waist and hip circumferences. ² Body temperature, blood pressure, pulse, respiratory rate. ³ Lipid profile (total cholesterol, LDL-cholesterol, HDL-cholesterol and triglycerides, serum/plasma, albumin, alkaline phosphatase, insulin-like growth factor 1 (IGF-1), Insulin-like growth factor-binding protein 1 (IGFBP1), creatinine, insulin, C-reactive protein (CRP),

aspartate aminotransferase (AST), alanine aminotransferase (ALT), homocysteine, glucose, glycosylated hemoglobin (HbA1c).

Screening and Baseline visit

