Potential participants already subjected to a 5-day fasting-mimicking diet (FMD) program either alone or in combination with the longevity diet previously enrolled in one of the two interventional arms and who completed the clinical study NCT05698654 less than three months before the enrolment period will be contacted *via* telephone to determine preliminary eligibility and interest. Once participants meet all inclusion/exclusion criteria, they will be offered by study staff the opportunity to learn more about the research opportunity before any procedure is performed. Participants meeting eligibility will be then invited to attend a baseline and two follow-up visits

Baseline visit will include measurement of height, weight, and vital signs (body temperature, blood pressure, pulse, respiratory rate), completion of medical history questionnaire, review of medical history and current medications, and collection of fasting blood (12 mL: 6 mL for serum, 6 mL for plasma). Blood testing will include: complete blood count (CBC), glycated hemoglobin (HbA1c), glucose, insulin, lipid profile (total cholesterol, LDL-cholesterol, HDL-cholesterol and triglycerides), AST (GOT), ALT (GTP), alkaline phosphatase, creatinine, reactive C protein (PCR), albumin, insulin, IGF-1, IGFBP1, homocysteine as well as a urine pregnancy test in females of child-bearing potential. Fasting is defined as 12 hours of refraining from consumption of food and beverages though unlimited consumption of water is allowed and encouraged. Participants will be given three boxes of FMD together with ketone test strips to self-monitor urinary ketone bodies during the FMD cycles. Detailed information on the FMD plans will be also given during the visit. Baseline visit will also include body composition assessment using Bioelectrical Impedance Analysis (BIA), measurement of height, weight, and vital signs, medical history, current medications and a collection of fasting blood for the genetic analysis (25 mL: 7.5 mL for serum, 7.5 mL for plasma, 10 mL for white blood cells). Note, the typical draw volume for blood donation in Italy is ~450 mL. Blood testing information will be also retried from the screening visit.

Follow-up visits

The follow-up visits will be carried out after three (follow-up visit 1) and five (follow-up visit 2) FMD cycles (6 and 12 months), in order to evaluate the progress of the trial.

Follow-up visit 1

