8.6. Study conclusions

Collected data from subjects will be reviewed to demonstrate that favourable changes are noted in biomarkers of body composition and age-related biomarkers with administration of the proprietary food products. Data will be evaluated for change from baseline over time within arms and for differences between the intervention arm and the control arm of previous study.

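### The primary analysis in 8.6.1 does not evaluate the primary endpoint in 2.2.1: it uses neither the previous trial's fat-mass loss nor the 50% threshold

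*Protocol*

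**What the plan says.** Protocol 2.2.1 defines the primary endpoint as "maintenance of at least 50% of the fat mass lost during the previous trial", measured after one year of follow-up cycles.

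Section 8.6.1 proposes mixed models to "compare the fat mass percentage change between the value measured at the end of the trial vs the baseline value". The model has "a fixed term modeling the change of fat mass between baseline and the second follow-up visit (after 1 year"), plus a random term for repeated measurements. The stated expectation is that "the coefficient associated with the fixed term (fat mass) will be either equal to zero (no change) or negative".

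Baseline here is the entry visit of the new study. Sections 3.1.1 and 3.2 say that assessments made at entry serve as its baseline, and section 3.3 and Table 1 schedule a fresh bioelectrical impedance (BIA) measurement at T0.

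Three other places touch the matter:
- Section 8.6 adds change from baseline within arms and "differences between the intervention arm and the control arm of previous study".
- Section 8.6.4 says that "the frequency and percentage of subjects reaching the primary endpoint will be presented by treatment group for each of the subgroups".
- Table 1 has a row for endpoint assessment at T0, T1 and T2.

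The interim efficacy analysis in 8.7 refers back to 8.6.1.

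**The concern.** To score the endpoint one needs fat mass at three times: the start of the previous trial, its end, and month 12 of this study. The 8.6.1 model uses only T0 and month 12. Any fat regained between the end of the previous trial and T0 is absorbed into the baseline and disappears from the analysis. The allowance of half the earlier loss, which the endpoint grants, does not appear either.

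The primary result could therefore be favourable when the endpoint is missed, or unfavourable when it is met. The interim analysis inherits the same problem.

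The unit is also open. The outcome in 8.6.1 can be read as percent change in kilograms of fat or as change in body-fat percentage, whereas the endpoint speaks of fat mass lost.

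**Working it through.** **Inputs from the protocol.** Endpoint: at least 50% of the previous loss kept at one year (2.2.1). Model: baseline to second follow-up visit, coefficient zero or negative (8.6.1). Previous arms: 167 and 167 (1.2). Drop-out: 21% and 18% (8.1). Maximum number of subjects: 267 (8.1). The protocol states no loss, regain, SD, alpha or power.

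**The plan's own figure.** 167 × 0.79 = 131.93 and 167 × 0.82 = 136.94. Rounded down, 131 + 136 = 267, as stated. This counts expected completers and is not a power calculation.

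**Endpoint against model.** Let L be the fat mass lost in the previous trial, g the share of L regained before T0, and h the share regained from T0 to month 12.
- Retention = 1 − g − h. The endpoint is met if g + h ≤ 0.5.
- Change from T0 to month 12 = h × L. Its sign depends on h alone.

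| g | h | Change T0 to month 12 | Retained | Endpoint |
|---|---|---|---|---|
| 60% | 0 | none | 40% | missed |
| 0 | 30% | increase | 70% | met |

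This step needs no assumed loss or SD.

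**Illustration 1: what a zero coefficient can hide.** Let D be month-12 fat mass minus the average of the previous trial's start and end values; the endpoint is met when D ≤ 0. With h = 0 and D normal, the proportion attaining is Φ((0.5 − g) × L / SD of D).
- L = 2 kg, SD 3 kg: g = 0 gives Φ(1/3) = 63%; g = 60% gives 47%; g = 100% gives 37%.
- L = 1 kg, SD 4 kg: 55% down to 45% over g = 0 to 100%.
- L = 3 kg, SD 2 kg: 77% down to 23%.

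The expected 8.6.1 coefficient is zero in every one of these cases.

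**Illustration 2: the converse.** Take g = 0, h = 30%, L = 2 kg, so the mean change is +0.6 kg. Assume SD 3 kg, a two-sided 5% paired test in kg, and n = 267 × 0.80 = 214. A significant increase appears in 83% of trials (noncentral t), although mean retention is 70% and Φ(0.2 × 2 / 3) = 55% of participants attain the endpoint. The 83% becomes 19% (L = 1 kg, SD 4 kg) to over 99% (L = 3 kg, SD 2 kg). One SD is used here for both D and the T0 to month-12 change, which is exact only if all participants lost the same amount.

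**Unit.** Going from 80 kg with 24 kg fat to 78 kg with 23.6 kg fat lowers fat mass by 0.4 kg, but body-fat percentage rises from 30.0% to 23.6/78 = 30.3%. The two readings of the outcome can differ in sign.

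**The case against.** **The endpoint is not absent from the analysis.** Table 1 schedules its assessment and 8.6.4 counts those who reach it. This is right and narrows the point: attainment per participant is clearly intended. But 8.6.4 is a descriptive tabulation by subgroup, and neither place gives an overall estimate or links attainment to the primary analysis.

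**Baseline might mean the start of the previous trial.** Sections 3.1.1 and 3.2 rule this out. Even on that reading the 50% threshold would not enter, and a zero coefficient would mean that the whole loss had been regained.

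**The T0 to month-12 trend serves the objective in 2.1.** It does, as a long-term trend. It still does not evaluate 2.2.1.

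**The risk is asymmetric.** With h = 0, a zero coefficient hides a failure of average retention only if more than half the loss returned before T0; below that, zero change is stricter than the endpoint. This stands. The documents give no g, the gap before T0 is limited to months, and 3.2 recruits people who achieved the previous study's objectives. High early regain is possible but not shown.

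**No test is stated.** Also correct: 8.6.1 gives an expectation, not an alpha or a sidedness, so the 83% rests on an assumed test. What remains is that the expectation carries no margin, so a non-significant coefficient would not by itself show maintenance.

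**Conclusion.** The concern holds and must be fixed. Section 8.6.1 fixes a model and a hypothesis for a different quantity from the endpoint in 2.2.1. This is a contradiction within the protocol, not detail left to an analysis plan: an analysis plan that followed 8.6.1 faithfully would analyse the wrong thing.

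The disagreement in both directions follows from algebra alone. How often it would occur in this trial cannot be derived, because the protocol gives no loss, regain or SD; the wide spread of the illustrations shows how much depends on those values. The difference in entry window (less than 6 months in 3.1.1 and 3.2, less than three months under the screening and baseline visit) is a separate contradiction to be reconciled and adds no weight here.

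**What to change.** **Change to 8.6.1.**
- Among participants with a previous-trial loss above zero, define attainment as month-12 fat mass ≤ 0.5 × (fat mass at previous start + fat mass at previous end), in kg.
- Make the overall proportion attaining, with its 95% confidence interval, the primary analysis, and also show it by previous arm.
- State how participants without a month-12 BIA count in the denominator.
- If a success claim is intended, fix in advance the minimum proportion that the lower confidence limit must exceed; the protocol gives none.
- Report mean D with its 95% interval as supportive only. If 40% lost 4 kg and keep 90%, and 60% lost 1 kg and keep 30%, mean D = 0.4 × (−1.6) + 0.6 × 0.2 = −0.52 kg, yet only 40% attain.
- Keep the T0 to month-12 model and the change from previous end to T0 as descriptive results.

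**Change to 8.7.** Use the same definition with the T1 BIA, labelled as a 6-month interim version of a one-year endpoint.

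**Cost.** Rewording, and linkage to BIA values that the endpoint already needs; no new visits. The drawbacks are these:
- *Exclusions.* Participants without an observed loss leave the primary analysis. With an assumed true loss of mean 2 kg and SD 2 kg, 21% are excluded at a BIA noise SD of 1 kg at both previous visits, and 25% at 1 and 2 kg. Recruiting only those who met the previous objectives (3.2) may lower this, but 3.1.1 does not list that condition.
- *Precision.* At about 70% attaining, the exact 95% interval is 63.5% to 76.1% (150 of 214), 62.7% to 76.9% (120 of 171) or 60.0% to 78.8% (70 of 100).
- *Denominator.* 150 of 214 is 70%; 150 of 267 is 56%.
- *Measurement noise.* With an assumed noise SD of 1 kg per visit, someone truly keeping 80% is classed as attaining with probability Φ(0.3 × L / √1.5): 60%, 69% and 84% for losses of 1, 2 and 4 kg.
- *Selection on observed loss.* If noise differs between the previous start and end visits, mean D shifts slightly: about 0.09 kg for noise SDs of 1 and 1.5 kg, and 0.21 kg for 1 and 2 kg, in a simulation under assumed values.
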